pRQ4: To what extent do children with a peer support group report a reduction in **bullying** at the end of the intervention compared to their pre-intervention baseline level?

sRQ5: To what extent do children with a peer support group report improved **mental health** at intervention end compared to their pre-intervention baseline level?

sRQ6: To what extent do children with a peer support group report better **quality of life** at intervention end compared to their pre-intervention baseline level?

sRQ7: To what extent do children with a peer support group report increased **general self-efficacy** at intervention end compared to their pre-intervention baseline-level?

sRQ8: To what extent does the effects as measured in R1-R7 persist 6- and 9 months after intervention end compared with pre-intervention baseline level?

sRQ9: To explore the recruitment rate and factors associated with non-participation, on school, provider, and child level.

sRQ10: To describe whether the intervention was delivered according to protocol in terms of quality, quantity, adaptions and variations across schools and time.

[figure not shown]
sRQ11: To describe the intervention acceptability from children's, teachers, school nurses and residents' perspectives.

sRQ12: To investigate barriers and facilitators to intervention delivery and the mechanisms of impact.

Study design

This is a cluster randomized trial of children in 5th to 7th grade in Norwegian primary schools with randomization at school level. The cluster design is well-suited due to the significant risk of contamination between the groups with a regular RCT design. The study flow is presented in figure 1. Intervention schools will implement the SFA-model for reducing bullying, whereas the control schools will offer usual care according to national guidelines. The intervention is at two levels; (i) training of school nurses and school staff and raising awareness about the SFA-model among parents and students; for this part the outcomes will be measured at cluster-level, and (ii) implementing the SFA-model on individual participant level; for this part the outcomes will be measured on individual level in the intervention cluster only. The recruitment process, the intervention and the outcomes measured are described below.

Figure 1 Study flow for the Cluster randomized controlled trial

Methods

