Recruitment and follow-up of children experiencing bullying: The first initiative for a support group may come from the child itself or other individuals concerned about the child's well-being. Initiating a dialogue is the first step in building trust and determining if a support group could help. The child, together with the school nurse or teacher, will assess whether the support group is suitable for them. The school nurse and teachers will evaluate the child's situation carefully before recommending a support group, and if necessary, they will explore alternative follow-up options, particularly for children with complex challenges. The child experiencing bullying will not be part of the support group but will be involved in the selection of peers and will agree on what can be shared about their story with the group. The school nurse or teacher will collaborate with the child to identify 5-7 peers who could be suitable to join the group. The child is individually followed with weekly consultations with the teacher or school nurse, using an SFA-counselling approach.

Recruitment and follow-up of peers in the support group: Once peers are chosen, they are invited to the group. In the support group children are asked if they are willing to help another child. Clear boundaries will be set for peer supporters, specifically on what they may and may not share with others. They brainstorm actions they can take in the upcoming week. This transforms the group into a catalyst for improving a child's situation through small initiatives, using fellow students as a resource for change (Heitmann et al., 2022). Weekly consultations with the child and the supporting group are set up to monitor progress and brainstorm further enhancements. Peers are encouraged to concentrate on improvements and will receive acknowledgement for their progress. Sessions usually last 15-30 minutes weekly until improvement is seen. Studies indicate that the situation often improves rapidly, and in many cases, 3-5 weeks is sufficient (Heitmann et al., 2022; Kvarme, Heitman, et al., 2022; Kvarme et al., 2016; Ma et al., 2021). A comprehensive implementation manual has been developed for this intervention, and key steps are presented in table 1.

Table 1 Overview of all steps in the intervention.

The solution-focused counseling approach (SFA) is used in each step

Step 1: Meeting with the child who needs help. Create hope and identify participants for the support group.

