^aCorresponding research questions, ¹ KIDSCREEN-27 (Haraldstad et al., 2011), ^{II} Olweus' questionnaire (Olweus., 2013), ^{III} Strength and Difficulties Questionnaires (Goodman, 1997). ^{IV}General self-efficacy scale (GSE) (Roysamb et al., 1998)

This instrument assesses various aspects of physical and psychological well-being, autonomy, parent relations, social support, peer support and the school environment in children and adolescents aged between 8 and 18 years. The questionnaire has been validated for use in Norwegian school children (Haraldstad et al., 2011). Additionally, the student survey (Elevundersøkelsen, UDIR) will be administered at class-level. This survey includes inquiries about inclusion and well-being within the school setting. Mental health will be evaluated using the Strength and Difficulties Questionnaires, a validated tool for children between aged 2-17 years (Goodman, 1999). To measure self-efficacy, the General Self-Efficacy scale (GSE) will be utilized. This scale captures one's confidence in dealing with various demanding situations. A validated 5-item version of the GSE is available for use with Norwegian schoolchildren (Roysamb et al., 1998).

Table 3 Process evaluation outline and outcomes.

Indicators	Data sources	Timing
Recruitment		
Number of eligible schools invited and numbers consenting to participation.	National data, project data, including socio-demographic information (e.g., school size, ethnicity, SES)	At study start
Number of possible participants at each school (school children), number of participants invited to attend activities, actual number who do attend each activity	Attendance records	Ongoing throughout the intervention period
Number who drop out (Bullied children and peers)	Attendance records and a survey to explore reasons	Ongoing throughout the project
What was delivered		
Number of activities delivered in terms of use of resources, training sessions, and resource use, training conducted and attendance at training	School action plan, school environment questionnaire, interviews with teachers and school nurses (intervention deliverers)	Monthly collection of logs/records, brief interviews at regular intervals throughout project and final exit interviews and school environment questionnaire (pre-, post-)
Description of unintended events		

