Log with unexpected side effects or outcomes from the intervention. Unexpected outcomes do not necessarily have to be negative. There may also be unanticipated positive health outcomes.	Survey with pupils, teachers and school nurse	monthly collection of attendance, exit survey

Participant satisfaction, acceptability and enjoyment		
Satisfaction/dissatisfaction with the programme	Interview with teachers and school nurses, focus groups. Pupils brief exit survey to all pupils, focus groups with teachers, school nurses.	Midpoint (brief) and exit
Promoting and inhibiting factors (with the context, program, organization and implementation)		
Understanding supporting networks		
What existing local infrastructure does schools (teachers/school nurse) perceive as useful to support the intervention. Which formal or informal networks exist and are used	Interview with teachers/school nurses of control and intervention schools	Midpoint and exit
Sustainability		
Whether plans have been made to continue with the intervention in some way	Interview with school leaders, teacher/school nurses	Exit interview

Safety Considerations

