
Follow-up of participants

All study support group participants will receive post-study follow-up consultations with the school nurse or social teacher after the intervention. *Adults for Children*'s experience with research involving children and will carefully address the ethical responsibilities, including how to inform children, in their 3-days training program. Participants from *Adults for Children* and the researchers are available for teachers, school nurses, children, and their parents throughout the study. A safety plan is also prepared for additional support should be necessary after the study concludes. If the intervention yields positive effects, all control schools will be invited to implement the intervention as per protocol soon after the conclusion of the study.

Data protection and statistical analysis

We will seek ethical approval for the study from the Regional Ethical Research Committee (REC) in South-East Norway and ensure compliance with data privacy regulations in line with NSD and EUs privacy regulation GDPR. Data will be collected through and stored in the secured server *Tjenester for Sensitive Data* (TSD), integrated solution for collecting and storing sensitive data, managed by the University of Oslo. This includes recording of interview-data through the use of Nettskjema-diktafon in TSD. This is in line with OsloMet's standards for confidentiality and data protection. A risk assessment with appropriate actions will be conducted prior to study implementation.

Baseline data will be presented descriptively. We will use 1600 children (9 schools in each arm) for comparison between intervention- and control schools on school-level. Generalized mixed models (GLM)

for repeated will be used to explore intervention outcomes on individual level for children who were targeted for support groups. GLM will also be used to analyse possible differences on school level. The results will be reported as the estimated between group changes with 95% confidence intervals.

For the process evaluation, descriptive statistical analysis of quantitative data and content analysis of qualitative data will be carried out.

Quality assurance

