Enrolling children in research raises a number of ethical concerns, including consent, confidentiality, and protection from harm (Powell et al., 2016). Children experiencing bullying are particularly vulnerable, underscoring the researchers' responsibility to prevent any additional risks. Conversely, their inclusion can empower children by giving them a voice. Chapter 9a of the Education Act, mandate schools to act if a student is experiencing an unsafe or unfavorable environment. In cases of social exclusion or feelings of loneliness, school nurses, in collaboration with the school staff, are obliged to intervene early at class-, group- or individual level. The support group intervention has the potential to directly benefit participants, aligning with the rights perspective. It can reinforce their sense of being valued individuals who are heard, offering opportunities for significant improvements in their own well-being. These benefits include increased opportunities to acquire knowledge, develop new skills, form new friendships, expand support networks, and have their concerns genuinely acknowledged and addressed. Given their unique perspective, individual children are able to evaluate potential risks to their own well-being. This underscores the importance of effectively communicating with the children, ensuring that they grasp the essence of the intervention and have a clear understanding of what is anticipated from their participation. All study materials will undergo quality assessments by *Adults for Children* to ensure their suitability for the intended age group in terms of language and content. Interpreter services will be made available for families who are not proficient in Norwegian. Children will be clearly informed that they have the right to discontinue the intervention at any point, without any obligation to provide a justification. They will still receive support as normal. Additionally, they will be provided with details regarding whom to contact and how, if they perceive any discomfort. Participants will be encouraged to seek help if an unmet need, such as a mental health concern, is identified. Peers will be supported regularly throughout the study. *Adults for Childrens'* experience with research involving children and will carefully address the ethical responsibilities, including how to inform children, in their 3-days training program.

References

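### Table 3's log is the only record designed for harm, yet it is worded for unexpected effects, good or bad, so harms the protocol foresees are not assured of being recorded or told apart

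*Protocol*

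**What the plan says.** **The log.** Table 3 (process evaluation) has one row on unintended events. Its content is "Log with unexpected side effects or outcomes from the intervention. Unexpected outcomes do not necessarily have to be negative". Its source is a survey of pupils, teachers and the school nurse, and its timing cell reads "monthly collection of attendance, exit survey".

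**Neighbouring records.** Table 3 also counts dropout among bullied children and peers, using "Attendance records and a survey to explore reasons", and collects satisfaction and dissatisfaction with the programme.

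**Risks the protocol has in view.**
- Study procedure, on the peers: "Clear boundaries will be set for peer supporters, specifically on what they may and may not share with others".
- Safety Considerations: children are told whom to contact if they feel discomfort, and are encouraged to seek help if an unmet need is found.
- The ethics text before the References: "Children experiencing bullying are particularly vulnerable", which it links to a duty to prevent further risk.

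**Individual scales.** Table 2 gives the Olweus questionnaire, KIDSCREEN-27, SDQ and GSE to participants who have a support group, at baseline, intervention end, 6 and 9 months. Study procedure says that the supported child is not a member of the group of peers.

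**Reporting.** For the models, Data protection and statistical analysis says: "The results will be reported as the estimated between group changes with 95% confidence intervals". For quantitative process data it plans descriptive statistics.

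**The concern.** A harm record depends on its entry rule. This one turns on whether an effect was unexpected, and it accepts good and bad effects alike. The events most worth counting in a peer-support intervention are the ones its designers already thought of, and those fit the rule least well. Staff in different schools could reasonably differ on whether to log a breach of confidence that the training warned them about. Mixing in positive surprises means that a total from the log has no clear meaning.

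This is protocol content. An analysis plan can decide how to tabulate events, but it cannot recover events that nobody wrote down. It matters because Follow-up of participants says that control schools will be invited to take up the intervention if effects are positive. That offer would rest on a benefit estimate without a readable count of negative events in vulnerable children and their classmates.

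**Working it through.** The protocol states no figure on this point, so the check is mainly one of setting sections side by side.

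**Step 1. Which records could hold a harm?**

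| Record | Designed for harm? | What it can miss |
|---|---|---|
| Log of unintended events (Table 3) | Yes | Foreseen events, if the wording is taken literally |
| Dropout with reasons (Table 3) | No | A child who worsens but stays; reasons may be absent, since Safety Considerations lets children stop without giving one |
| Satisfaction and dissatisfaction (Table 3) | No | It records opinion of the programme, not events |
| Repeated scales (Table 2) | No, these are efficacy outcomes | Peers, and any event that is not a scale score |
| Whole-class survey (Table 2, Study 1) | No | Described as anonymous, so not traceable to a particular child |

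The arrangements in Safety Considerations and Follow-up of participants (contact details, emergency measures, safety plan) concern care. They do not say what is recorded or reported.

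**Step 2. Test the entry rule on the foreseen events.**
- A peer shares a child's story beyond the agreed limits. The protocol sets those limits, so the event is anticipated. It is unintended, but hardly unexpected.
- A child feels discomfort. The protocol provides for this. Same result.
- Bullying starts or gets worse. The protocol does not list this as a side effect, but it is the adverse direction of the main outcome, in children for whom further risk is acknowledged. For a supported child it may show on the Olweus score. For a peer it has no individual measure.

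In each case the row heading (unintended) points towards logging, and the row content (unexpected) points away from it. The row does not settle which governs.

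**Step 3. How many children depend on the log?** Inputs: 60 supported children (Sample size calculation, individual child level) and 5 to 7 peers per child (Study procedure). Assume one group per supported child.

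60 × 5 = 300 and 60 × 7 = 420 peer places.

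These are places, not distinct children, because one pupil may sit in more than one group. For all of them the log is the only purpose-built harm record, and no repeated individual scale backs it up.

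**Step 4. Can negative entries be separated afterwards?** The row allows positive entries and requires no field for direction, affected child or role. Descriptive statistics on such a log can give a total, but the protocol does not assure a count of negative events or of children affected.

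**The case against.** The best case for the plan has four parts.

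1. *The row is headed by unintended events.* A breach of confidence or worse bullying is plainly unintended, no section bars it from the log, and the protocol sets up no formal expected/unexpected classification. This stands. A reader might infer that foreseeable harm would go unreported; the text supports only that recording is not assured.

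2. *Other records exist.* Dropout reasons and dissatisfaction data can carry harm. This also stands: the log is not the only place where harm could appear. It is the only one designed for it.

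3. *Worsening would show in the outcomes.* A reader might infer from questions worded as "To what extent do children with a peer support group report a reduction in" bullying that only improvement can be reported. That goes too far. An estimated change with a 95% confidence interval would show average worsening too. For supported children it could not be attributed to the intervention, because they are measured in intervention schools only.

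4. *The foreseen harms are thinly stated.* The limit on sharing is preventive, the remark on discomfort is conditional, and the remark on vulnerability is general. This is fair, and it is a reason to name the events rather than leave staff to infer them.

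A further tempting step is to count children who score below their own baseline. With 55 children, a 3-point mean gain, two-sided 5% and an assumed 80% power (none is stated at child level), the implied SD of change is 3 × √55 / (1.960 + 0.842) = 7.94. Under a normal distribution Φ(−3/7.94), about 35%, would score lower even if the target were met. This is not evidence of harm or of a defect. It includes measurement error, has no control group, and would arise in any trial that reports a mean. The 3 points are an anticipated group mean change in one KIDSCREEN-27 domain, not a threshold for an individual child. Whether to tabulate such children belongs in the analysis plan, which is not at hand.

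**Conclusion.** The point holds as one about the entry rule and structure of the log. The only record designed for harm is worded so that events the protocol itself has in view need not be entered, and so that negative entries need not be distinguishable from positive ones. The exposure is 60 planned supported children and 300 to 420 peer places. Peers depend on the log most, because they have no repeated individual scales.

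The conclusion rests on reading the row's content literally. If staff follow the heading instead, much would be captured, but the good and bad entries would still be mixed. No number of missed events can be derived from the protocol, and none is claimed. The point does not extend to the planned models or to the care arrangements. The change is worth making before data collection.

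**What to change.** In Table 3, in the row on unintended events:

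- Change the entry rule to all negative events in supported children and in peers, whether or not expected. Name at least disclosure beyond the agreed boundaries, discomfort, and new or worse bullying.
- Log unexpected positive outcomes as a separate item.
- State that negative events will be reported as number of children and number of events, separately for supported children and peers.

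No individual cut-off on a scale is needed, and no change to clinical follow-up is proposed. The cost is a few lines of wording and slightly more logging, within the existing log and surveys and with no extra visits or participants.

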The target population for the study are all school children in 5th-7th grade in primary schools in Asker, Moss and Lillestrøm municipalities in the central-eastern part of Norway. Primary schools with more than 200 students and with a school nurse appointed in at least 50% position are eligible for the study. Eligibility for having a support group established is based on the subjective experience of loneliness by the individual child and is defined as a negative emotional state caused by the discrepancy between the desired and actual social relationships, in line with Peplau et al (1).

Clusters and randomization procedure Since decisions about bullying interventions are typically made at the municipal level, we will begin the recruitment process of schools through enrolment of selected municipalities, as illustrated in figure 2. In selected municipalities consenting to participate, we will randomly invite 26 primary schools from the pool of eligible primary schools in these municipalities.

Figure 2. Illustration of the recruitment process of primary schools in xx, xxx and xxx municipalities in Norway

We will continue enrollment until the pre-identified number of schools is reached. The enrolled schools will be sorted by size and then block-randomized in a 1:1 ratio to either the intervention arm (hereafter referred to as intervention schools) or the control arm (hereafter referred to as control schools). A statistician not involved in the study will carry out the randomization procedure. After randomization, the schools will be informed about their assigned cluster and will receive more detailed information accordingly.

Sample size calculation *School level*: Based on the available literature, we anticipate that 6-10% of children in 5th -7th grade will report bullying (Krusell et al., 2019; Wendelborg, 2021). This proportion is expected to be reduced to at least 6 % in intervention schools' post-intervention. With a significance level at 5% and power at 80%, we will need 721 children in each arm. Accounting for additional variation, we would need 793 in each arm. We assume there will be three classes in each school with about 30 children in each class. Thus, we aim to include 26 schools (13 for each arm) to ensure that the study is sufficiently powered.

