Since all children in the study are younger than 16 years of age, consent will be sought from both parents and children who participate in the support group, followed by informed assent by children in all 5ths–7th grade in intervention and control schools. Informed consent will also be sought from parents and children participating in peer support groups (intervention schools). For parents of children in 5-7 classes who do not participate directly in the support group, passive consent will be obtained. In this part of the research, no personally identifiable information will be collected. The questionnaire is anonymous and no name, personal number or other directly identifiable information is asked. No one in the municipality, neither teacher, school nurse, administration staff or others will have access to answers that can be used to identify what individuals have answered. The results will be published through statistics showing how children and young people responded, or how different groups responded (boys or girls). Obtaining consent from all parents for students in the 5th–7th grade is a demanding process that will represent an additional burden and work for the schools. However, every student in 5th–7th grade will be informed of their right to refuse participation or to only assent to certain areas of the survey. They will also be informed that they are free to withdraw from the study at any time. The questionnaire will be conducted in the classroom with a teacher or school nurse present, and there will be minimal risk of being exposed to discomfort, stress, and injury. There will be no direct intervention or interaction. The researchers will conduct thorough research on ethical assessments of risks and develop concrete measures in terms of emergency response.

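### The anonymous all-pupil survey is to be reported as between-group changes, but the 721 per arm was computed for a one-wave comparison that carries no baseline sampling error

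*Protocol*

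**What the plan says.** Table 2 gives the all-pupil survey at baseline, intervention end, 6 months and 9 months, and assigns pRQ1-3 and sRQ8 to it. Safety Considerations says of this part that "The questionnaire is anonymous and no name, personal number or other directly identifiable information is asked". No pupil code is described anywhere in the protocol.

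The section on data protection and statistical analysis names a repeated-measures model for the support-group children. For the schools it says "GLM will also be used to analyse possible differences on school level", and it closes with "The results will be reported as the estimated between group changes with 95% confidence intervals".

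The school-level sample size calculation starts from "we anticipate that 6-10% of children in 5th -7th grade will report bullying" and continues "This proportion is expected to be reduced to at least 6 % in intervention schools". It then states "With a significance level at 5% and power at 80%, we will need 721 children in each arm" and "Accounting for additional variation, we would need 793 in each arm". Allocation is "block-randomized in a 1:1 ratio", by school.

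**The concern.** Study design says that support-group outcomes are measured in the intervention schools only. A between-group result can therefore come only from the anonymous survey. The wording of pRQ1 (a reduction in bullying) and of sRQ8 (persistence against the pre-intervention level) also points towards change.

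A difference in change subtracts two sampled baselines from two sampled follow-ups. The sample size calculation contains two sampled proportions, not four. If the final report follows the analysis sentence literally, three primary questions are answered with a contrast for which the trial was not sized, on data for which no linkage is described. Whether pupils can be linked is settled when the baseline is collected. A later analysis plan cannot restore it.

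**Working it through.** **Inputs from the protocol.** Significance level 5% (two-sided reproduces the N), power 80%, 721 and 793 per arm, rates 10% and 6%. Only the upper end of the 6-10% range reproduces the N. Analysis set: 1600 children, so 800 per arm, in 9 schools per arm. Recruitment target: 13 schools x 3 classes x 30 = 1170 per arm. The analysis set and the target disagree, which is a separate matter; both are carried here.

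**Assumptions.** Baseline 10% in both arms, control rate constant, equal numbers at each wave. The allowance for additional variation (793/721 = 1.10) is read as a design effect.

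**1. The plan's own figure.** n = [1.96 x sqrt(2 x 0.08 x 0.92) + 0.8416 x sqrt(0.10 x 0.90 + 0.06 x 0.94)]² / 0.04² = (0.7520 + 0.3220)² / 0.0016 = 720.9, so 721. Then 721 x 1.10 = 793. Both match.

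**2. Variance of the two contrasts, per effective child per arm.**
- One wave: 0.0900 + 0.0564 = 0.1464.
- Difference in change, independent waves: 3 x 0.0900 + 0.0564 = 0.3264.
- Ratio: 0.3264 / 0.1464 = 2.23.

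**3. Power if the waves are treated as independent.** SE = sqrt(0.3264 / n_eff); power = Φ(0.04/SE − 1.96).

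| Per arm | n_eff (÷1.10) | SE | Power, change | Power, one-wave |
|---|---|---|---|---|
| 793 | 721 | 0.0213 | 47% | 80% |
| 800 | 727 | 0.0212 | 47% | 80% |
| 1170 | 1064 | 0.0175 | 63% | 93% |

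Without the design effect, the change contrast has 50%, 51% and 67%. For 80% it would need (1.96 + 0.8416)² x 0.3264 / 0.0016 = 1601.2, so 1602 independent children per arm per wave.

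**4. Power if school is the unit and the same pupils answer twice.** A school's change in prevalence needs no pupil identifier, and its spread between schools already reflects repeat responders. Let ρ be the within-pupil correlation, k the schools per arm and m the pupils per school.
- Change: SE = sqrt{1.10 x [0.18(1−ρ) + 0.1464 − 0.1425ρ] / (km)}, noncentral t on 2k−2 degrees of freedom. The 0.1425 is 2 x sqrt(0.09 x 0.0564).
- Follow-up adjusted for school baseline: SE = sqrt{1.10 x 0.1464 x (1−ρ²) / (km)}, noncentral t on 2k−3. This ignores the cost of estimating the slope, about two points at 9 schools per arm.

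| Schools x pupils per arm | ρ | Change | Adjusted follow-up |
|---|---|---|---|
| 9 x 89 | 0 | 43% | 75% |
| 9 x 89 | 0.3 | 56% | 79% |
| 9 x 89 | 0.5 | 70% | 86% |
| 9 x 89 | 0.7 | 89% | 96% |
| 13 x 90 | 0 | 59% | 90% |
| 13 x 90 | 0.3 | 74% | 93% |
| 13 x 90 | 0.5 | 87% | 96% |
| 13 x 90 | 0.7 | 98% | over 99% |

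The ρ values are an illustrative range. All pupils are assumed to answer at both waves; turnover would move the results towards the ρ = 0 rows.

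**5. Sensitivity to the intraclass correlation (ICC).** A design effect of 1.10 at 90 pupils per school implies ICC = 0.10/89 = 0.0011. Take larger values, with an assumed school-level correlation between waves (CAC) of 0.8, 9 schools of 89 per arm, and a normal approximation. The change variance is 0.3264 x [(1−ICC)/m + ICC(1−CAC)]/k. The adjusted variance is 0.1464 x [1+(m−1)ICC] x (1−r²)/(km), with r = m x ICC x CAC/[1+(m−1)ICC].
- ICC 0.02: change 40%, adjusted follow-up 55%.
- ICC 0.05: change 31%, adjusted follow-up about 40%.

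Power falls for both, but the adjusted contrast stays ahead.

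**The case against.** **The 80% is not wrong.** A reader might infer that the trial's power is really 47% instead of 80%. The documents do not support that. The 80% was computed for a one-wave comparison and is correct for it, and the protocol never claims it for a difference in change. This stands in full.

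**The analysis is not firmly fixed.** The school-level sentence speaks only of differences, pRQ1-3 compare arms at named follow-up times, and the sentence on changes may be loose wording. How baseline enters the model could be left to an analysis plan. This stands in part. The sentence is still the only statement of what will be reported, and a between-group result can come only from the survey.

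**Unlinked does not mean independent.** A reader might infer that any unlinked change analysis has 47% power. It does not: step 4 shows that school-level changes gain from repeat responders without any identifier. The 47% holds only when waves are treated as independent, and only at 793 to 800 per arm. The protocol's correlation of 0.7 cannot settle the gain either. It is stated for a KIDSCREEN-27 domain in children experiencing loneliness, not for a bullying item in all pupils, so no standard-error inflation for this survey can be derived from it.

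**Linkage is not expressly excluded.** A reader might infer that the survey cannot be linked. The text excludes names, personal numbers and other directly identifying data. A self-generated code is neither described nor ruled out, although calling the survey anonymous makes one doubtful.

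**Conclusion.** The concern holds as a mismatch between three parts of the protocol: an anonymous survey with no linkage described, results announced as between-group changes, and a sample size for one wave. A difference in change carries baseline sampling error that the 721 does not cover; with independent waves its variance is 2.23 times that of the one-wave contrast.

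Under the stated assumptions, that means about 47% power at 793 to 800 per arm and 63% at 1170. If the same pupils answer repeatedly and school is the unit, power is higher, by an amount that the documents do not allow one to fix. In every scenario computed, the follow-up difference adjusted for school baseline had more power than the change contrast. This is an inexpensive improvement to the analysis wording, not a demonstrated failure of the stated power.

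**What to change.** In the section on data protection and statistical analysis, for pRQ1-3:

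- Replace the reporting of between-group changes with the arm difference at each follow-up wave.
- Adjust that difference for the school's own baseline value of the outcome and for the size ordering or block used in randomisation, with school as the cluster.
- State that the all-pupil survey is analysed as repeated cross-sections unless a pseudonymous code is used. If a code is intended, Safety Considerations must say so before the baseline is collected.

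The change uses only data already planned and the size ordering already used in randomisation. It needs no pupil identifier, no change to consent and no additional pupils, and it brings the reported contrast back to the comparison for which 721 was computed. A pupil code would cost more, because the anonymity statement would have to be revised; it is not required.
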